6.1.5 Treatment duration

The planned duration of aGvHD treatment is 24 weeks (approximately 6 months).

The Treatment Period for each patient will begin on Study Day 1 and continue until the end of Week 24, unless treatment change for any reason including treatment failure, e.g. aGvHD progression, mixed response, or no response, or aGvHD flare failure as defined in [Section 8.4.1.2](#), intolerable toxicity, death, or withdrawal from the study for other reasons occurs.

During the Treatment period, and beyond Day 28, patient's treatment will be managed according to their response as follows:

For patients with response at Day 28 (see [Table 8-3](#)):

- Patients responding to ruxolitinib will continue ruxolitinib until Day 56. These patients may be tapered off ruxolitinib as needed, starting no earlier than Day 56. The dose tapering strategy should be based on evaluation of the condition of the subject, current dosing regimen and the clinical judgment of the Investigator. (see [Section 6.1.5.1](#).)
- If a taper of ruxolitinib is considered appropriate, the taper should be completed no later than Week 24 unless prolonged tapering is indicated due to an aGvHD flare or other safety concern (see [Section 6.1.5.1](#)).

For patients with a lack of response at Day 28 (see [Table 8-3](#)):

- Patients must discontinue study treatment and be treated per Investigator's judgement. These patients will then enter the long-term follow-up period.

Patients responding to treatment will be tapered off immunosuppression (corticosteroids and CNI) as described in [Section 6.1.5.1](#).

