This open-label, single-arm, Phase I/II multi-center study will investigate the PK, activity and safety of ruxolitinib added to the patient's immunosuppressive regimen in infants, children, and adolescents ages ≥ 28 days to < 18 years old with either grade II-IV aGvHD or grade II-IV SR-aGvHD. This trial will utilize age groups: Group 1 includes patients ≥ 12 y to < 18 y, Group 2 includes patients ≥ 6 y to < 12 y, Group 3 includes patients ≥ 2 y to < 6 y, and Group 4 includes patients ≥ 28 days to < 2 y. Patients will remain in the age group throughout the study based on the age at the time of start of treatment. Enrollment initiation into the youngest age group, Group 4 (Phase I/II) will be subject to the review of available PK, safety, and activity data in consultation with the data monitoring committee (DMC), Pediatric Committee (PDCO), and a final decision by the Sponsor.

All patients will be enrolled and treated for 24 weeks (approximately 6 months) or until early discontinuation. All patients will also be followed for an additional 18 months (total duration = 2 years from enrollment). Should the occurrence of aGvHD flare require treatment re-initiation

or should ruxolitinib not be discontinued by the end of 24 weeks due to extended tapering, patients may continue taper ruxolitinib beyond 24 weeks up to a maximum of 48 weeks. As patients ≥ 12 y to < 18 y are already being included in [CINC424C2301], and treated with 10 mg BID, this dose is the recommended phase II dose (RP2D), and will be used to treat all patients in this age group. For the Phase II, all other age groups will be treated with the RP2D determined during the Phase I. Therefore, all ≥ 12 to < 18 year old patients will automatically be enrolled in the Phase II. It is planned that the first 5 patients treated in Group 1 will undergo extensive PK sampling to inform the RP2D determination of the younger age groups in the Ph I. Additional patients may undergo extensive sampling should one or more of the first 5 patients not be evaluable or until the dose/exposure is confirmed.

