3.1.1 General definitions

Investigational drug and study treatment

Investigational drug/study treatment, will refer to the ruxolitinib in this single arm study.

Date of first administration of study treatment

The date of first administration of study treatment is derived as the first date when a nonzero dose of study treatment was administered as per the DAR eCRF. The date of first administration of study treatment will also be referred as *start of investigational drug*.

Date of last administration of study treatment

The date of last administration of study treatment is defined as the last date when a nonzero dose of study treatment was administered as per DAR eCRF. The date of last administration of study treatment will also be referred as *end of investigational drug*.

Study day

The study day, describes the day of the event or assessment date, relative to the reference start date.

The study day is defined as:

- The date of the event (visit date, onset date of an event, assessment date etc.) – reference start date + 1 if event is on or after the reference start date;
- The date of the event (visit date, onset date of an event, assessment date etc.) – reference start date if event precedes the reference start date.

The reference start date for all assessments (e.g. safety, efficacy, PK, [REDACTED], etc.) is the start of study treatment.

The study day will be displayed in the data listings. If an event starts before the reference start date, the study day displayed on the listing will be negative.

Time unit

A year length is defined as 365.25 days. A month length is 30.4375 days (365.25/12). If duration is reported in months, duration in days will be divided by 30.4375. If duration is reported in years, duration in days will be divided by 365.25.

Baseline

For safety and efficacy evaluations, the last available assessment on or before the date of start of study treatment is defined as “baseline” assessment.

If patients have no value as defined above, the baseline result will be missing.

On-treatment assessment/event and observation periods

The overall observation period will be divided into three mutually exclusive segments:

1. ***pre-treatment period***: from day of patient’s informed consent to the day before first administration of ruxolitinib
2. ***on-treatment period***: from date of first administration of study treatment to 30 days after date of last actual administration of ruxolitinib (including start and stop date)

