3. ***post-treatment period***: starting at day 31 after last administration of ruxolitinib.

Safety summaries (tables, figures) include only data from the on-treatment period with the exception of baseline data which will also be summarized where appropriate (e.g. change from baseline summaries). In addition, a separate summary for death including on-treatment and post-treatment deaths will be provided. In particular, summary tables for adverse events (AEs) will summarize only on-treatment events, with a start date during the on-treatment period (***treatment-emergent*** AEs).

However, all safety data (including those from the post-treatment period) will be listed and those collected during the pre-treatment and post-treatment period will be flagged.

Windows for multiple assessments

In order to summarize data collected over time (including unscheduled visits), the assessments will be time slotted. The following general rule will be applied in creating the assessment windows: If more than one assessment is done within the same time window, the assessment performed closest to the target date will be used. If two assessments within a time window are equidistant from the target date, then the earlier of the two assessments will be used. If multiple assessments on the same date then the worst case will be used. Data from all assessments (scheduled and unscheduled), including multiple assessments, will be listed.

The following time windows are defined for descriptive summaries on aGvHD assessment, biomarkers and safety ([Table 2-1](#)) by visit. The end of treatment assessment will be mapped into the time points as appropriate.

Table 2-1 Time windows for aGvHD assessment, [REDACTED] and safety assessment (lab, vital sign, growth, etc.)

Time Window	Planned Visit Timing	Time Window Definition
-------------	----------------------	------------------------

On treatment

Baseline (Day 1)	On or before Study Day 1	≤ Study Day 1
Week 1	Study Day 7	Study Days 4 – 10
Week 2	Study Day 14	Study Days 11 – 17
Week 3	Study Day 21	Study Days 18 – 24
Week 4	Study Day 28	Study Days 25 – 31
Week 5	Study Day 35	Study Days 32 – 38
Week 6	Study Day 42	Study Days 39 – 45
Week 7	Study Day 49	Study Days 46 – 52
Week 8	Study Day 56	Study Days 53 – 59
Week 12	Study Day 84	Study Days 71 – 98
Week 16	Study Day 112	Study Days 99 – 126
Week 20	Study Day 140	Study Days 127 – 154
Week 24	Study Day 168	Study Days 155 – 182
Week 28	Study Day 196	Study Days 183 – 210

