3.2.1 Subgroup of interest

Efficacy

The primary efficacy endpoint will be summarized by the following subgroups to examine the homogeneity of treatment effect using EES:

- Age group (range defined in [Table 1-1](#))
- Age group and formulation (tablet, capsule, liquid)
- Diagnosis (treatment naïve aGvHD and SR-aGvHD)
- [REDACTED] No formal statistical test of hypotheses will be performed for the subgroups, only point estimate of the treatment effect and 90% confidence intervals will be provided.

Safety

Key safety analyses will be repeated on the Safety Set in the following subgroups:

- Age group (range defined in [Table 1-1](#))
- Age group and formulation (Tablet, capsule, liquid)
- Diagnosis (treatment naïve aGvHD and SR-aGvHD)
- [REDACTED]

The objective for carrying out these subgroup analyses is to identify potential safety issues that may be limited to or more commonly observed in a subgroup of patients.

The following summaries will be presented by age group, formulation and [REDACTED] only subgroup:

- Overview of adverse events
- Adverse events by preferred term
- Adverse events with suspected relationship to study treatment by preferred term
- Serious AEs, irrespective of causality, by preferred term
- Adverse events leading to study treatment discontinuation by preferred term
- Overview of adverse events of special interest
- On-treatment deaths
- All study deaths

The following summaries will be provided by age group and and by treatment-naive vs SR aGvHD:

- Overview of adverse events
- AEs, irrespective of causality, by primary system organ class and preferred term
- AEs with suspected relationship to study treatment, by primary system organ class and preferred term
- Serious AEs, irrespective of causality, by primary system organ class and preferred term
- Serious AEs with suspected relationship to study treatment, by primary system organ class and preferred term
- On-treatment deaths, by primary system organ class and preferred term
- Overview of adverse events of special interest

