3.4 Treatments (study treatment, rescue medication, concomitant therapies, compliance)

3.4.1 Study treatment / compliance

Duration of exposure in days to ruxolitinib will be summarized by age group and by means of descriptive statistics. It will also be categorized into time intervals; frequency counts and percentages will be presented for the number (%) of patients in each interval.

Total daily dose, actual cumulative dose, dose intensity (DI) and relative dose intensity (RDI) will be summarized for ruxolitinib by age group.

The number (%) of patients who have dose reductions or interruptions, and the reasons, will be summarized for ruxolitinib by age group.

Patient level listings of all doses administered on treatment along with dose change reasons will be produced by age group.

The Safety Set will be used for all summaries and listings of study treatment.

If more than one dose and/or formulation is assigned within one age group, then summaries and listings will be reported by age group as well as doses/formulations within the age group.

Duration of exposure to study treatment

Duration of exposure to study treatment (days) = (last date of exposure to study treatment) – (date of first administration of study treatment) + 1.

Summary of duration of exposure of study treatment in days will include categorical summaries (based on clinically meaningful time intervals) and continuous summaries (i.e. mean, standard deviation etc.) using appropriate units of time.

Duration of exposure in patient-years

The duration of exposure in patient-years is a total of the duration of exposure in years from all the patients in the agegroup.

Duration of exposure to systemic corticosteroid

Duration of exposure to systemic corticosteroid treatment (days) = (last date of exposure to systemic corticosteroid) – (date of first administration of systemic corticosteroid) + 1.

Duration of exposure to systemic corticosteroid in patient-years

The duration of exposure to systemic corticosteroid in patient-years is a total of the duration of exposure to systemic corticosteroid in years from all the patients in the age group.

Duration of exposure to CNIs

Duration of exposure to CNI treatment (days) = (last date of exposure to CNI) – (date of first administration of CNI) + 1.

Duration of exposure to CNI in patient (years)

The duration of exposure to CNI in patient-years is a total of the duration of exposure to CNI in years from all the patients in the age group.

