3.8.1 Adverse events (AEs)

For reporting of AEs the overall observation period will be divided into mutually exclusive categories, including pre-treatment, on-treatment, post-treatment periods as defined in [Section 2.1.1](#).

[figure not shown]
AE summaries will include all AEs occurring (new or worsening) during on-treatment period. All AEs collected in the AE eCRF page will be listed along with the information collected on those AEs e.g. AE relationship to study drug, AE outcome etc. AEs with start date outside of on-treatment period will be flagged in the listings.

AEs will be summarized by number and percentage of patients having at least one AE, having at least one AE in each primary system organ class (SOC) and for each preferred term (PT) using MedDRA coding. A patient with multiple occurrences of an AE will be counted only once in the respective AE category. A patient with multiple CTCAE grades for the same preferred term will be summarized under the maximum CTCAE grade recorded for the event. AE with missing CTCAE grade will be included in the ‘All grades’ column of the summary tables.

In AE summaries, the primary system organ class will be presented alphabetically and the preferred terms will be sorted within primary SOC in descending frequency. The sort order for the preferred term will be based on the descending frequency in all patients.

The following adverse event summaries will be produced by group; overview of adverse events and deaths, AEs by SOC and PT, summarized by relationship (all AEs and AEs related to study treatment), seriousness (SAEs and non-SAEs), leading to treatment discontinuation, leading to dose interruption/adjustment, and leading to fatal outcome.

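### Safety subgroup tables compare crude on-treatment AE percentages although time at risk is tied to Day 28 response, so a difference between subgroups may reflect unequal exposure

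*SAP*

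**What the plan says.** SAP 3.2.1 gives the purpose of the safety subgroup tables as to "identify potential safety issues that may be limited to or more commonly observed in a subgroup of patients". It lists AE, related-AE, SAE, AESI and death tables by age group, formulation and diagnosis.

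SAP 3.8.1 sets the measure: "AEs will be summarized by number and percentage of patients having at least one AE". Under SAP 3.1 the denominator is the number of patients in the population or subgroup. SAP 3.1.1 defines the on-treatment period as "from date of first administration of study treatment to 30 days after date of last actual administration of ruxolitinib", and the AE tables "will summarize only on-treatment events, with a start date during the on-treatment period".

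Time on drug depends on response. For lack of response at Day 28, Protocol 6.1.5 says "Patients must discontinue study treatment and be treated per" the investigator's judgement. Otherwise "The planned duration of aGvHD treatment is 24 weeks (approximately 6 months"), and SAP section 2 adds that "patients may continue taper ruxolitinib beyond 24 weeks up to a maximum of 48 weeks" after a flare or a delayed taper.

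SAP 3.4.1 derives person-time ("The duration of exposure in patient-years is a total of the duration of exposure in years"), but only by age group and only to describe exposure. It is not used as an AE denominator, and exposure by diagnosis is not planned.

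Three planned summaries are less dependent on the window or independent of it:
- SAP 3.8.4.3: cumulative incidence of grade ≥3 infection by age group and diagnosis, with death and treatment discontinuation as competing risks.
- Protocol 12.5.2: Grade 2–3 infections over Day 1 to Day 56. SAP 3.8.1.1 instead summarises infection severity over the on-treatment period.
- SAP 3.2.1: all study deaths in the age-group and formulation tables.

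**The concern.** Asking whether an event is more common in one subgroup is a comparison of risk, and crude percentages are comparable only if the subgroups were watched for similar lengths of time. Here the length of observation follows from outcome. A subgroup with more Day 28 non-responders, or more early stopping for any other reason, has less time in which to record an AE.

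The error can go either way. Equal hazards would show as an apparent excess in the longer-treated subgroup, and a real excess in the shorter-treated subgroup could be hidden. By diagnosis, the reader would have no exposure figures with which to notice.

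**Working it through.** The plan prints no figure for this point, so the windows are derived from its rules.

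**Windows (last dose + 30 days)**
- Stop at Day 28: 28 + 30 = Day 58
- 24 weeks: 168 + 30 = Day 198
- 48 weeks: 336 + 30 = Day 366
- Ratios: 198/58 = 3.4 and 366/58 = 6.3

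Day 58 is the response-driven short end and not a minimum: a single dose gives Day 31, and death is shorter still.

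**Artefact under identical hazards.** Let F(d) be the probability of at least one AE by day d, and p the risk by Day 198. With a constant hazard, λ = −ln(1 − p)/198 and F(d) = 1 − exp(−λd). The crude percentage is ORR × F(responder window) + (1 − ORR) × F(58), so the spurious gap is

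(ORR_A − ORR_B) × [F(responder window) − F(58)].

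Example with p = 0.50: λ = 0.00350 and F(58) = 0.184. For ORR 80% against 55%, the gap is 0.25 × (0.500 − 0.184) = 7.9 points (43.7% against 35.8%).

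The response contrasts and p are assumptions. The documents supply 80% (sample-size assumption), 55% and 50–60% (Protocol 12.8.1) and 62% (phase III trial, Protocol 1.1.2.1.2), but none as a contrast between these subgroups.

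| ORR contrast | Responder window | Gap, p = 0.20 to 0.70 |
|---|---|---|
| 80% v 55% | 198 days | 3.4 to 10.1 points |
| 80% v 62% | 198 days | 2.5 to 7.3 |
| 60% v 50% | 198 days | 1.4 to 4.0 |
| 80% v 55% | 366 days | 6.9 to 14.9 |
| 80% v 55%, front-loaded AEs (Weibull shape 0.5) | 198 days | 2.2 to 5.5 |
| 80% v 80% | either | 0 |

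The 366-day row puts every responder on 48 weeks, which the protocol reserves for flare or delayed taper. It is an upper bound.

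**Sampling error.** Protocol Amendment 3 gives 45 patients, 29% treatment-naïve and 71% steroid-refractory, so about 13 and 32. The standard error of a difference is √[p(1 − p)(1/13 + 1/32)]: 13.2 points at p = 0.20 and 16.4 at p = 0.50.

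**Would an exposure-adjusted rate settle it?** With a constant hazard, yes: at p = 0.50 both subgroups show 127.9 per 100 patient-years. With front-loaded AEs (shape 0.5), ORR 85% against 62% and identical hazards, patients with an event divided by time to first event or end of window gives 150.8 against 163.8. That is 163.8/150.8 = 1.086, a spurious 8.6% excess in the poorer-responding subgroup.

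**Would the SAP 3.8.4.3 method settle it?** Only at early times. It treats discontinuation as a competing event, so a Day 28 non-responder contributes F(28) and no more. At p = 0.50, F(28) = 0.093 and F(168) = 0.445, so at Day 168 the 80% v 55% gap is 0.25 × (0.445 − 0.093) = 8.8 points. At 1 month the subgroups stand on nearly the same footing.

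**The case against.** The strongest reply is that nothing in the documents predicts a response difference. Protocol 12.8.1 cites 50–60% for both de novo and steroid-refractory disease and no association between response and age. Protocol 1.2 expects a similar safety profile in the two diagnoses. This stands. A reader might infer that treatment-naïve patients will respond better and so show more AEs, but the documents do not support that. The point is conditional. SAP 3.2.1 does itself plan to examine response by diagnosis and age, so equality is not taken for granted either.

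The size also shrinks under moderate assumptions:
- If the pooled ORR is 80% and naïve patients have 85%, the refractory rate is (45 × 0.80 − 13 × 0.85)/32 = 78%, and the gap at p = 0.50 is 2.2 points. With naïve at 90%, refractory is 76% and the gap 4.4.
- For 85% against 62% the gap is 7.3 points. A mean responder window of 142 days, midway between Day 86 (last dose Day 56) and Day 198, cuts it to 4.8. Front-loaded AEs cut it to 4.3. Those two rates pool to 68.6%, below the planned 80%.

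The tables are descriptive screens with no test between subgroups, and sampling noise is the larger problem. That stands too, and it limits the importance of the point. Noise does not cancel a systematic tilt, however, and the reader can see the sample sizes but not the exposure by diagnosis.

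A reader might also infer that the plan has no safety analysis that accounts for time. That is wrong: grade ≥3 infections have one, all-study deaths are not limited to the window, exposure by age group is reported, and SAP 3.10 plans exposure–safety modelling. The opening of the AESI section is redacted, so AESI methods can be judged only from the visible text.

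**Conclusion.** The point holds as an interpretive weakness. The AE, SAE, related-AE and AESI subgroup tables use crude percentages over a window tied to response, so they cannot by themselves show that an event is more common in one subgroup.

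If response or treatment duration differs between subgroups, the artefact is 1.4 to 10.1 points with a 198-day responder window under the assumed contrasts. It reaches 14.9 points if all responders stay on for 48 weeks, falls to about half to two-thirds with front-loaded AEs, and is zero if response and duration are equal. At a 198-day window it is below the standard error for 13 against 32 patients. For age group and formulation the mechanism is the same, but no document figure suggests a contrast.

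It would be too strong to say that the subgroup safety results will be misleading, or that the trial's efficacy conclusions are affected.

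**What to change.** In SAP 3.2.1 and 3.8.1, for the treatment-naïve against steroid-refractory tables, and for age group and formulation where exposure differs:

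1. Add a common fixed-window version of the AE overview, SAE, preferred-term and AESI outputs. Day 1–28 is the cleanest: even one dose gives a window to Day 31, so only death, withdrawal or loss shortens it. Day 1–56, the protocol's own infection window, is an alternative. A last dose before Day 26 ends the on-treatment window before Day 56 (26 + 30 = 56), so the number not observed to Day 56 should be shown.
2. Alternatively, extend the SAP 3.8.4.3 cumulative-incidence method to these AEs and compare subgroups at 1 month. If later times are wanted, state how discontinuation is handled, since counting it as a competing event keeps the dependence on time on drug.
3. Show exposure duration and patient-years by diagnosis beside the tables.
4. Exposure-adjusted rates may be added as a supplement, with the constant-hazard assumption stated.
5. State that subgroup comparisons are read from item 1 or 2, and that crude on-treatment percentages are descriptive.

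The cost is SAP wording and a few extra tables from data already collected, with no change to conduct. Intervals will be wide, and a fixed window leaves out later events, so the full on-treatment tables should stay.
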